## **Statistical Analysis Plan (SAP):**

Intention-to-treat strategy will be used in this study. Intention-to-treat strategy will be used in this study. Statistical analysis will be achieved with SPSS, version 26.

Categorical variables will be presented as proportion and percent. Continuous variables will be presented as mean (standard deviation) for parametric data or as a median (25th-75th percentile) for non-parametric data.

Regarding baseline characteristics, Kruskal-Wallis or ANOVA test (depending on type of data and the continuous data distribution (normal or not)) will be used to compare these characteristics between the study groups. We will report the P-value for our statistical tests with level of statistical significance will be P-value  $\leq 0.05$ .

In case of existing differences in some baseline characteristics, logistic regression will be performed. This allows studying the effect of these variables on the primary outcomes of the study to exclude the effect of these confounding variables and to ensure the effect on the outcomes is due to interventions.

Regarding the outcomes, we will compare the 28-day all-cause mortality rate, result of PCR test at hospital discharge and incidence of infusion related or hypersensitivity reactions during and after the end of drug infusion (primary outcome) using the Kruskal-Wallis test with reporting the P-value.

While the secondary outcomes (hospital stay duration, icu stay duration and others) are compared using Kruskal-Wallis or ANOVA test depending on type of data and the distribution of data (normal or not)

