#### 2-Clinical Efficacy

Percentage of patients with one or more medically attended visits

- Symptoms offset at day 7

Safety is measured as

Percentage of treated patients who experience infusion related and hypersensitivity reactions and incidence of any serious and unexpected adverse effect.

This previous study(9) concluded that efficacy is greater and more obvious in seronegative outpatients (whose immune response is not developed yet to produce antibodies against virus) and with high baseline viral load outpatients.

Now, data(10) is available for these new antibodies cocktails. The U.S. Food and Drug Administration (FDA) has allowed an Emergency Use Authorization (EUA) for casirivimab and imdevimab combination in the treatment and post-exposure prophylaxis of mild to moderate COVID-19 in adults and pediatric outpatients (more than 12 years of age and not less than 40 kg) with positive Polymerase Chain Reaction (PCR) results of direct SARS-CoV-2 viral testing, and who are at high risk for progression to severe COVID-19 requiring hospitalization or causing death.

In contrast, REGN3048 and REGN3051 are still not authorized for use in patients(10):

- who are hospitalized due to COVID-19, OR
- who require oxygen therapy due to COVID-19, OR
- who require an increase in baseline oxygen flow rate due to COVID-19 in those on chronic oxygen therapy due to underlying non-COVID-19 related comorbidity(10).

Now, casirivimab and imdevimab are approved investigational antibodies, Serious and unexpected adverse effects can occur that not previously reported with their use(10).

Confirmed adverse effects include hypersensitivity and infusion related reactions and the study have showed that there is no difference in safety profile between intravenous (I.V) infusion and subcutaneous (S.C) injection. Data about use during pregnancy and breastfeeding mother is insufficient yet. Also, Data not support any dosage adjustment in hepatic and renal patients (10).

This antibody combination follows linear pharmacokinetics after its single intravenous doses with half-life of about 25 to 37 days for both antibodies. Regarding elimination, this combination is not metabolized by liver cytochrome enzymes ,and not excreted by kidneys (10).

Limitations of previous study include

1-short duration of follow up

2-not used much clinical relevant outcomes like mortality rate

3- Not studied the long term effect of antiviral efficacy in lowering viral load on inflammatory markers.

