## **Interventions:**

Population included in this study will be assigned into 3 groups with 1:2:2 ratios to receive either antibodies cocktail or standard antiviral therapy (remdesvir, favipravir) as shown in table2 and figures 2 & 3.

Group A patients will receive REGN3048-3051(Antibodies cocktail (casirivimab and imdevimab) ) in low-dose regimen 1.2 gm (1200 mg of combined antibodies) diluted in 250 ml 0.9% sodium chloride solution as single I.V infusion over 30-60 minutes.

Group B patients will receive Remdesivir :

Day1 (loading dose): 200 mg (two 100mg vials) diluted in 500ml 0.9% sodium chloride solution infused I.V over 60 minutes

Day 2-5 or Day 2-10 (maintenance dose): 100 mg (one 100mg vial) in 250 ml 0.9% sodium chloride solution infused I.V over 30 minutes

Group C patients will receive Favipravir :

[figure not shown]
Day 1 (loading dose): 1600 mg (8 tablets) or 1800 mg (9 tablets) orally or in Ryle tube / 12 hours

Day 2-5 or day 2-10 (maintenance dose): 600 mg (3 tablets) or 800 mg (4 tablets) orally or in Ryle tube / 12 hours

[figure not shown]
Patients will be received standard of care by Physicians, Clinical pharmacist , Nurses and as guided by Egyptian COVID-19 treatment protocol.

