## **Outcomes:**

Parameters that will be assessed during hospitalization at day 0(baseline), day 3, 7, 14, 28 include:

- C-reactive protein (CRP)
- ferritin
- lactate dehydrogenase (LDH)
- D-dimer
- serum creatinine(S.Cr) and estimated creatinine clearance(CrCl)
- alanine aminotransferase (ALT), aspartate aminotransferase (AST), albumin, bilirubin

Clinical outcomes measured before & during intervention

1) Primary outcomes

- 1- 28-days mortality rate (efficacy).
- 2-PCR test results at end of hospital visit (efficacy).
- 3-precentage of patients who developed infusion related or hypersensitivity reactions during and after the end of drug infusion and reporting of any Serious and unexpected adverse events may occur that have not been previously reported with REGEN-COV use that may cause drug discontinuation (Safety).

2) Secondary outcomes

- 1-Need for invasive mechanical ventilation.
- 2- Invasive mechanical ventilation and oxygen support duration (days).
- 3- Time to clinical improvement (defined as 2 points reduction in the WHO disease ordinal progression scale(11&12) or discharge, whatever happens first)
- 4- ICU and hospitalization length of stay (days).
- 5- SOFA score(13) on day 0,3,7,14, and 28.
- 6- COVID19 WHO disease progression score(11&12) from day 0 to day 28.
- 7- Inflammatory markers including CRP, ferritin, LDH
- 8- liver and kidney functions

In addition to clinical outcomes measured before and during intervention, Vital signs, glasgow coma score (GCS),complete blood count (CBC), artierial blood gas (ABG) and prothrombin time (PT) is recorded at day0.

Patients' charactrestics(age,gender) and relevant medical and medication history and current COVID-19 treatment drugs will be recorded on admission

Duration of research will be about 6 months from Novmber 2021 to March 2022

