## **Sample Size:**

A total sample sizes of 246 patients would achieve at least 80 % power to detect a risk difference of 0.2 (20%) in the 28-day all-cause mortality (primary outcome) with a significance level ( $\alpha$ ) of 0.05 and 95% confidence level using the ANOVA or Kruskal-Wallis test of independent proportion in G\*Power software. To compensate for the estimated loss-to-follow-up and increase the study power, we will increase the sample size in both remdesivir and favipravir groups to be 106 patients compared to 53 patients in Antibodies cocktail Group As Antibodies cocktail product is available for only about 50 COVID-19 patients. In addition, the ratio (1:2:2) is the closest to reality according to number of patients who receive each drug.

The mortality data was estimated from the average mortality in August, September, and October 2021 at the Mansoura University Isolation Hospital among all hospitalized patients. Mortality rate is found to be about 360 cases in these 3 months (120 cases / month). The online system has been used to obtain mortality rate in these three months.

The current admission rate at the Mansoura University – Isolation Hospital is 250 cases per month on average; our needed sample is about 250 cases.

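### Intention-to-treat is the only analysis set, so the primary safety outcome (infusion-related and hypersensitivity reactions) has no treated-patient denominator

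*Combined protocol and SAP*

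**What the plan says.** The Statistical Analysis Plan section gives one analysis principle, printed twice in succession: "Intention-to-treat strategy will be used in this study". It is not restricted to any outcome. The same section then compares 28-day mortality, PCR result at discharge and the "incidence of infusion related or hypersensitivity reactions during and after the end of drug infusion (primary outcome) using the Kruskal-Wallis test", all in one sentence.

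The Outcomes section lists this as the third primary outcome: the percentage of "patients who developed infusion related or hypersensitivity reactions during and after the end of drug infusion", together with serious and unexpected adverse events. It does not say which patients form the denominator.

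The Introduction, when it describes the earlier outpatient study of the cocktail, gives that study's safety measure as "Percentage of treated patients who experience infusion related and hypersensitivity reactions". That denominator is not carried into this plan.

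On group sizes, the Sample Size section plans to "increase the sample size in both remdesivir and favipravir groups to be 106 patients", "compared to 53 patients in Antibodies cocktail Group", and gives as the reason that "Antibodies cocktail product is available for only about 50 COVID-19 patients". The Interventions section assigns patients "with 1:2:2 ratios to receive either antibodies cocktail or standard antiviral therapy". The Population section instead speaks of randomisation at 2:1:1, and the Method section calls the study non-randomised.

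**The concern.** Intention-to-treat suits mortality because it keeps the comparison between the groups as assigned. It suits an acute reaction to a drug less well, because only a patient who was given the drug can react to it.

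Under the rule as written, two things would follow whenever the drug assigned and the drug received differ:

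- A patient assigned to the cocktail but never infused would remain in the cocktail denominator.
- A reaction to a drug other than the assigned one would be reported under the assigned group.

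Safety is the second of the study's two aims, and this outcome is one of three named primary outcomes. A rate per patient assigned does not answer the question a reader would bring to it, which is how often patients given the cocktail react.

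**Working it through.** **Plan's own figures.** The group sizes reproduce: 1:2:2 applied to 265 gives 265 × 1/5 = 53 and 265 × 2/5 = 106 for each comparator. The only power figure, 246 patients in the Sample Size section, concerns mortality. It reproduces as a three-group ANOVA with Cohen's f = 0.2 (244, rounded up to 3 × 82 = 246) and has no bearing here. The documents give no expected reaction rate and no power for the safety outcome, so every reaction rate below is an assumption.

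**Inputs.** Planned cocktail group: 53 (Sample Size; Table 2). Cocktail supply: about 50 (Sample Size). Let m be the number assigned to the cocktail but not infused, and r the reaction rate among those infused. Neither is given in the documents.

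**Dilution.** If undosed patients have no counted reaction, the rate by assigned group is r × (53 − m)/53, and the relative understatement is m/53.

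| m (assumed) | (53 − m)/53 | Relative understatement | Shown if r = 10% |
|---|---|---|---|
| 0 | 1.000 | 0% | 10.0% |
| 3 | 50/53 = 0.943 | 5.7% | 9.4% |
| 5 | 48/53 = 0.906 | 9.4% | 9.1% |
| 10 | 43/53 = 0.811 | 18.9% | 8.1% |

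The row m = 3 is what results if about 50 is read as exactly 50. The row m = 0 is what results if the supply covers all 53.

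**Undosed patients given another study drug.** Suppose the 3 receive remdesivir, with an assumed 2% reaction rate. The rate by assigned group is then (50 × 0.10 + 3 × 0.02)/53 = 5.06/53 = 9.5%.

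**A single misattributed reaction.** It moves the cocktail percentage by 1/53 = 1.9 points.

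**Effect on power.** Take 10% against 2% (cocktail against remdesivir), two-sided 5%, by the normal approximation for two proportions. With m = 3, power is 56% by assigned group (53 against 106, rates 9.43% and 2%) and 59% among those treated (50 against 106, rates 10% and 2%). Expected events are few (about 5 and 2), so these values are rough; the gap of about 3 points is the useful part.

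**Direction.** It is not fixed. Undosed cocktail patients lower the cocktail rate. Undosed patients in a comparator group lower that group's rate: with 5 of 106 undosed and r = 2%, 0.02 × 101/106 = 1.9%, which slightly widens an apparent cocktail excess. A cocktail-assigned patient who reacts to a different drug raises the cocktail rate.

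**The case against.** The strongest reply is that assigned and received may be the same thing in this study. The Method section calls it non-randomised, and the Sample Size section justifies 1:2:2 by how many patients get each drug in practice. If groups are formed by the drug given, an intention-to-treat analysis and an analysis by drug received coincide at the start of treatment. This stands as a possibility. It does not settle the matter, because the Population section says patients are randomised and the Interventions section says they are assigned. Even if groups are formed by receipt, nothing is said about a study drug given later.

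A reader might infer from 53 planned against about 50 available that three cocktail patients will go undosed. The documents do not support this. The supply is the stated reason for the small cocktail group, and about 50 is compatible with 53.

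A reader might also infer that reactions after a switch will be charged to the wrong drug. No section provides for switching, the cocktail is a single infusion, and earlier use of remdesivir or favipiravir is an exclusion criterion. Misattribution is a consequence of the rule if a switch occurs, not a feature of the plan.

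Nor do the documents say that undosed patients are coded as reaction-free. There is no coding rule, and the outcome's wording presupposes an infusion. What remains after these points is that the only stated rule covers this outcome and no other denominator is offered.

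It is also fair to say that a treated-patient set leaves another denominator problem untouched. Favipiravir is given by mouth or tube, so its group cannot have a study-drug infusion reaction. That is a separate matter.

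**Conclusion.** The point holds in a conditional form. The plan applies intention-to-treat to the whole study, including the primary reaction outcome, and defines no treated-patient safety set. That is a stated rule ill-suited to the outcome, not merely a missing detail.

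The size depends on how many patients do not receive the drug assigned, which the documents do not give. At 3 of 53 undosed with no counted reactions, the understatement is 5.7% in relative terms, and it is zero if every patient is dosed as assigned. Larger gaps, such as 5 or 10 undosed, are assumptions with no support in the text.

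It would go too far to say that the rule always hides a safety difference, since undosed comparator patients or a reaction to a non-assigned drug can move the comparison the other way. The change is worth making because the outcome is primary and the correction is cheap, not because a material bias has been shown.

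**What to change.** In the Statistical Analysis Plan section, limit intention-to-treat to the efficacy outcomes and add wording to this effect:

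*The third primary outcome and all other adverse events will be analysed in all patients who received any amount of a study drug. Each patient is counted once, under the first study drug actually received. Patients given more than one study drug, and reactions that occur after a later study drug, are listed separately.*

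Counting each patient once matters. Entering a patient under every drug received would put one person in two groups of a Kruskal-Wallis comparison that needs independent groups.

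The Population, Method and Sample Size sections should also be reconciled on how groups are formed, since this decides what assignment means.

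The cost is small but not nil. The study drug actually given and its date must be recorded; the Outcomes section describes recording current COVID-19 drugs on admission and does not mention later changes. The safety comparison would also no longer be by assigned group, so any protection from random allocation, if there is any, would be lost for that outcome.

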## **Population:**

265 COVID-19 PCR confirmed patients with indication for antiviral therapy is included in this study and will be randomized (2:1:1) into 3 groups

1- Group A: REGN3048-3051(Antibodies cocktail (casirivimab and imdevimab) )

2-group B: Remdesivir

3-group C: Favipravir

Population in this study are patients hospitalized in isolation hospital- Mansoura university.

A computer file containing a written informed consent from included patients will be provided. Paper will not be a tool for providing agreement by patients or their relatives to avoid transmission of infection.

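### Adjustment of 28-day mortality depends on a baseline significance check, with no named covariates and no governing result; a short list fixed in advance would recover power under random allocation and leave less bias from the listed factors otherwise

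*Combined protocol and SAP*

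**What the plan says.** All of the analysis text is in the Statistical Analysis Plan section.

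- Baseline characteristics are compared across the three groups by Kruskal-Wallis or ANOVA. The general significance level is 0.05.
- The regression is conditional: "In case of existing differences in some baseline characteristics, logistic regression will be performed". Its stated purpose is "to exclude the effect of these confounding variables and to ensure the effect on the outcomes is due to interventions".
- Mortality, the PCR result and infusion or hypersensitivity reactions are compared as the "primary outcome) using the Kruskal-Wallis test with reporting the P-value".

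No covariate is named, and nothing says which result counts if the unadjusted test and the regression disagree. The Outcomes section lists the day-0 data to be collected but ties none of it to the model.

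The Sample Size section states that 246 patients "would achieve at least 80 % power to detect a risk difference of 0.2 (20%) in the 28-day all-cause mortality", then sets the groups at 53, 106 and 106. It gives no control-group rate, only local counts: "Mortality rate is found to be about 360 cases in these 3 months (120 cases / month"), and an admission rate that "is 250 cases per month on average; our needed sample is about 250 cases".

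The allocation method is unresolved. Under Population, patients "will be randomized (2:1:1) into 3 groups"; under Interventions, they "will be assigned into 3 groups with 1:2:2 ratios". The Method section calls the study not a randomised controlled trial, and Sample Size ties 1:2:2 partly to how many patients receive each drug in practice.

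**The concern.** A baseline test answers the wrong question. It asks whether groups differ by more than chance, not whether the factor predicts death. A strong predictor with a modest imbalance can be left out, and a weak one with a chance imbalance can be put in.

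What is at stake depends on allocation. If it is random, there is no bias to remove, but prognostic information already collected goes largely unused in a trial whose unadjusted test is below its planned power. If it is not random, group A may be less sick by an amount that the baseline tests miss, and part of that difference is then read as a drug effect. Because neither the covariates nor the governing result is fixed, both could be chosen after the results are known.

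**Working it through.** **Inputs from the documents.** Groups 53/106/106, alpha 0.05, risk difference 0.20, N = 246, 120 deaths and 250 admissions per month.

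**Assumed.** Mortality 120/250 = 48% in B and C; flagging at P <= 0.05 (an inference from the SAP's general level); prognostic strength and size of imbalance.

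**1. The plan's own figure.** One-way ANOVA with three groups and f = 0.20: non-centrality 246 x 0.20^2 = 9.84, power 80.4%. The 246 reproduces. It also equals 40% against 20% with 82 per arm (3 x 82 = 246).

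**2. Unadjusted power at the actual group sizes, 28/48/48%.** Pooled rate (53 x 0.28 + 212 x 0.48)/265 = 116.6/265 = 0.44. Non-centrality = [53 x 0.16^2 + 212 x 0.04^2]/(0.44 x 0.56) = 1.696/0.2464 = 6.88. With 2 df, power is 64.8%. At 20/40/40% it is about 68%.

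**3. Chance that the baseline test flags a factor shifted by d SD in group A.** Non-centrality = (53 x 212/265) d^2 = 42.4 d^2.

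| d (SD) | non-centrality | power |
|---|---|---|
| 0.30 | 3.82 | 39% |
| 0.40 | 6.78 | 64% |
| 0.48 | 9.77 | 80% |
| 0.50 | 10.60 | 83% |

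**4. How often the rule acts under random allocation.** Each given factor is flagged about 5% of the time. Outcomes names about 16 day-0 items individually. If they were independent, at least one would be flagged in 1 - 0.95^16 = 56% of trials; across simulations with independent or correlated items the figure was roughly 40-60%. The regression is often triggered, but mostly by whichever variable happened to differ.

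**5. Simulated power under random allocation.** 48% mortality, A 20 points lower, one factor, 3,000 trials per setting:

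| OR per SD | Kruskal-Wallis | conditional rule | always adjusted |
|---|---|---|---|
| 2.2 | 66.9% | 67.2% | 74.2% |
| 3.3 | 67.1% | 67.6% | 80.4% |
| 5.0 | 66.5% | 67.3% | 83.4% |

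A separate simulation with five covariates gave 67/67/73% at AUC 0.68, 65/66/77% at 0.76 and 66/67/81% at 0.82. With useless or weak covariates (AUC 0.50-0.62) it gave 66-68/66-69/67-71%, a gain of about 1-3 points.

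**6. Simulated bias under non-random allocation, no drug effect.** This takes the regression as governing once triggered.

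- One factor (OR 2.2-5.0 per SD), A less sick by 0.3-0.5 SD: the rule leaves 0.7-3.3 points and rejects in 4.9-6.7% of trials; always adjusting leaves 0.4 or less and rejects in 4.7-6.1%.
- Four or six factors correlated at 0.4 (OR 1.6, 0.2-0.3 SD): the rule leaves 1.0-2.5 points and rejects in 4.5-5.9%; always adjusting leaves 0.2 or less.
- Four or six independent factors all favouring A (OR 1.6-2.0): the rule leaves 3.8-8.6 points and rejects in 7.1-16.5%; always adjusting leaves 0.3 or less. The five-covariate simulation gave 3.1-7.8 points for the rule.

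**7. A confounder outside a fixed list.** Here a six-covariate model omits one measured factor that is shifted by 0.5 SD. Two separate simulations gave 7.9 and 7.2 points of bias for the fixed model, against 1.1 and 0.5 for the SAP rule. At 0.3 SD, the first gave 4.2 against 1.6.

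**8. Model size.** With 8 terms: 0.48 x 265/8 = 15.9 deaths per term; at 30% mortality, 0.30 x 265/8 = 9.9.

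**The case against.** The strongest counter-argument concerns the remedy. In steps 5 and 6 the always-adjusted model contains every simulated factor, so its freedom from bias is close to automatic. A closed list can do worse than the SAP rule when a measured factor outside it is imbalanced, as step 7 shows. This stands. It limits the bias claim to listed covariates and is why the fix includes a sensitivity model.

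A reader might infer that the trigger would rarely fire. The documents do not support that: with about 16 baseline items some difference is flagged in roughly 40-60% of trials. What is rare is the flagging of any given prognostic factor.

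A reader might also infer that the unadjusted test governs throughout, so that severity differences pass entirely into the drug effect. The SAP does not say which result governs, but it gives control of confounding as the regression's purpose, so the natural reading is that the regression governs once triggered. On that reading false positives stay near 5-7% for one factor or correlated factors.

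The power gain depends on covariate strength. Six correlated factors gave 89.5%, but together they act like one score with an OR of about 7.3 per SD, so I do not rely on that figure. Part of any gain also reflects a slightly liberal test. The shortfall from 80% is mainly a matter of sample size and group sizes. The 48% divides August-October deaths by a current admission rate, and the exclusion of patients expected to die within 48 hours may lower it.

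**Conclusion.** The concern holds in a bounded form. The SAP ties adjustment to a baseline check that does not measure prognostic importance, and it leaves the covariates and the governing result open.

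- **Random allocation:** no bias, but power of about 65-70% under the rule against about 73-84% with moderate to strong covariates always in the model. The gain is only 1-3 points if they are weak.
- **Non-random allocation:** roughly 1-3 points of residual bias for one factor, and about 4-9 if several independent factors all favour group A. A pre-named model removes this only for the covariates it contains.

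These sizes rest on the assumed 48% mortality, prognostic strengths and imbalances, and on reading the trigger as P <= 0.05. The direction under random allocation does not depend on the exact values, provided the covariates are prognostic.

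This should be fixed. A reader might infer that confirmed non-random allocation makes it critical. The results do not support automatic escalation: with one factor or correlated factors, false positives barely differ between the two approaches, and unlisted or unmeasured confounding would remain under either.

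**What to change.** Delete the baseline-difference trigger as the condition for adjustment and state, before outcome data are seen:

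- The governing analysis of 28-day mortality is a logistic regression with treatment group (two terms) and a short fixed covariate list, whatever the baseline P-values. An example is age, gender, day-0 WHO progression score and day-0 SOFA score, plus one or two day-0 laboratory values chosen by the investigators. All are already listed for collection under Outcomes.
- Treatment is tested by the 2-df likelihood-ratio test at 0.05. A standardised risk difference is reported with a 95% CI. The unadjusted Kruskal-Wallis test is supporting.
- A sensitivity model adds any other collected baseline factor that is imbalanced in size, such as LDH, ferritin, D-dimer, medical history or concurrent COVID-19 drugs.
- Missing baseline covariates are filled by simple imputation, so that no patient is dropped for them. With six covariates each 5% missing, complete cases would keep only 0.95^6 = 73.5%, or 195 of 265. The handling of missing 28-day status is also stated.
- If the study is non-randomised, both models are reported together and the claim "to exclude the effect of these confounding variables and to ensure the effect on the outcomes is due to interventions" is softened.

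Reconcile Population, Interventions, Method and Sample Size on whether, and in what ratio, patients are randomised. The text above applies to mortality only. PCR at discharge first needs a rule for deaths before discharge, and infusion reactions may be too rare for such a model.

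Cost: SAP wording, two models, an interval for the risk difference and a simple imputation, with no new data. Downsides: with 8 terms the test is slightly liberal (about 5.6-6.5% under no effect), and confounding by unmeasured or unlisted factors remains if allocation is not random.

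### If baseline differences trigger it, logistic regression is also applied to the reaction outcome with no sparse-data method, so the adjusted comparison with an empty arm would be unusable

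*Combined protocol and SAP*

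**What the plan says.** The Outcomes section makes the percentage of "patients who developed infusion related or hypersensitivity reactions during and after the end of drug infusion" the third primary outcome, beside 28-day mortality and the PCR result. The SAP section gives these three outcomes two analyses.

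- **Main comparison.** All three, reactions included, are compared across the groups by an unadjusted Kruskal-Wallis test with a P-value.
- **Conditional adjustment.** "In case of existing differences in some baseline characteristics, logistic regression will be performed". The SAP continues: "This allows studying the effect of these variables on the primary outcomes of the study". It gives the purpose as removing confounding, so that an effect on the outcomes can be attributed to the interventions. No primary outcome is excepted.

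The SAP names SPSS 26. It gives no covariate list, no limit on covariates relative to events, no penalised or exact regression, and no rule for an arm without events.

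On group sizes, the Sample Size section says "we will increase the sample size in both remdesivir and favipravir groups to be 106 patients" and, for the cocktail, "compared to 53 patients in Antibodies cocktail Group". No section gives an expected reaction rate.

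**The concern.** Reactions may be few, and the cocktail arm is small. When an arm has no events, the maximum-likelihood odds ratio against that arm is infinite or zero. Software then stops at an arbitrary large coefficient with a huge standard error, and the Wald P is close to 1. This happens in the pattern that matters most for the second study aim, the safety of the cocktail: reactions on the cocktail and none on a comparator.

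The trigger is likely to be met. The Method section calls the study non-randomised (the Population section says randomised), the Sample Size section ties the group sizes to product supply and usual prescribing, and many baseline variables are to be tested at 0.05. Because the regression is there to rule out confounding, a small unadjusted P followed by an adjusted P near 1 could be read as confounding having accounted for the excess. The adjusted P would in fact carry no such information.

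**Working it through.** **Inputs.** Arm sizes are 53, 106 and 106, total 265 (Sample Size section and Table 2). The reaction rate r is not in the documents, so a range is assumed. The plan states no figure on this point to reproduce.

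**Step 1: chance of an empty arm at the same rate in all arms.**
P(no events in n patients) = (1 − r)^n. Write a = (1 − r)^53 and b = (1 − r)^106.
At least one comparator empty: 1 − (1 − b)². Any arm empty: 1 − (1 − a)(1 − b)².

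| Assumed r | Expected reactions (265r) | Cocktail arm empty (a) | One comparator empty (b) | At least one comparator empty | Any arm empty |
|---|---|---|---|---|---|
| 1% | 2.65 | 59% | 34% | 57% | 82% |
| 2% | 5.30 | 34% | 12% | 22% | 49% |
| 3% | 7.95 | 20% | 4% | 8% | 26% |
| 5% | 13.25 | 7% | 0.4% | 1% | 7% |

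The column for at least one comparator is the relevant one, because an empty cocktail arm cannot mask harm from the cocktail.

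**Step 2: unequal rates.** Favipiravir is given by mouth or tube (Interventions section), so that arm cannot have an infusion reaction to study drug, although hypersensitivity remains possible. Assume 5% on the cocktail, 5% on remdesivir and 0.5% on favipiravir:
1 − (1 − 0.95^106)(1 − 0.995^106) = 1 − (1 − 0.0044)(1 − 0.5878) = 0.59.

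**Step 3: what each analysis reports for 3/53, 0/106, 0/106.** The logistic model contains arm only, by maximum likelihood, with favipiravir as reference.

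| Analysis | Result |
|---|---|
| Kruskal-Wallis (planned, unadjusted) | P = 0.0024 |
| Logistic, Wald, cocktail v favipiravir | coefficient 18.4, SE about 3,904, P = 0.996 |
| Logistic, likelihood ratio for arm | P = 0.0075 |
| Exact three-group test | P = 0.0076 |
| Fisher, cocktail v remdesivir | P = 0.036 |

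The exact three-group P is (53·52·51)/(265·264·263) = 0.0076, since all three reactions falling in the cocktail arm is the least probable table. The coefficient and SE depend on where the iterations stop, which shows that no finite estimate exists. The Kruskal-Wallis P is smaller than the exact P because its chi-square approximation is poor here: the expected counts are 3 × 53/265 = 0.6 and 3 × 106/265 = 1.2 in each comparator.

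**Step 4: how far the failure reaches.** With 5/1/0 events, the Wald P for cocktail v favipiravir is 0.996, while Kruskal-Wallis gives 0.0004. With 5/1/1 the model is estimable and the same Wald P is 0.031. Only contrasts with an empty arm fail.

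**Step 5: allocation ratio.** The Interventions section says "Population included in this study will be assigned into 3 groups with 1:2:2 ratios", but the Population section says "will be randomized (2:1:1) into 3 groups". The steps above use the first, which agrees with Table 2 and the Sample Size section. Under 2:1:1 the arms would be about 132, 66 and 66 (265/4 ≈ 66). At 1% the cocktail arm would be empty 0.99^132 = 27% of the time, and at least one comparator 1 − (1 − 0.99^66)² = 1 − (1 − 0.515)² = 76% of the time. The two ratios need to be reconciled, but the point stands under either.

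**The case against.** A reader might infer that the plan as a whole would miss a reaction excess. The documents do not support that. The regression is conditional and supplementary, and nothing says that it replaces the Kruskal-Wallis comparison, which flags the example at P = 0.0024. Categorical data are also to be shown as proportions, so 3/53 against none would be visible. This part of the objection stands.

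Four further points also stand.

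- The model does not fail as a whole: only contrasts with an empty arm diverge, and a likelihood-ratio test for arm remains usable (P = 0.0075). The SAP does not specify one, nor does it specify Wald tests.
- That the regression is ordinary maximum likelihood is an inference, though the natural one where nothing else is named.
- That empty arms will be frequent depends on a rate the documents do not give. At 5% in every arm, some arm is empty only 7% of the time and a comparator only 1%.
- Equal-rate figures describe how often estimation breaks down, not how often true harm is masked, since at equal rates there is no harm to mask.

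It can also be said that a standard error in the thousands warns any analyst. That is fair, but a pre-specified analysis should not depend on someone noticing it and then choosing a substitute after seeing the data.

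**Conclusion.** The point holds in a limited form. The SAP's conditional regression covers the reaction outcome, is likely to be triggered, and has no provision for sparse events. Where a comparator arm is empty, the adjusted contrast with it has no finite estimate and a Wald P near 1. The unadjusted result is unaffected, so what is at risk is the adjusted safety result and how it is interpreted.

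The chance of an empty comparator is 57%, 22%, 8% and 1% at equal assumed rates of 1%, 2%, 3% and 5%, and about 59% if favipiravir has 0.5% and the other two arms 5%. These figures rest on assumed rates, arms of 53/106/106, independent patients, and maximum-likelihood fitting with Wald inference. At equal rates of 5% or more the problem is uncommon. This is a cheap improvement to the SAP.

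**What to change.** Amend the SAP section as follows.

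1. Limit the regression triggered by baseline differences, in its ordinary form, to 28-day mortality and the PCR result.
2. For reactions, report counts and percentages by arm with an exact three-group (Fisher-Freeman-Halton) test.
3. If an adjusted estimate for reactions is wanted, pre-specify Firth-penalised logistic regression with profile-likelihood limits and very few covariates named in advance.

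The cost is a few lines of wording, with no change to patients, data or sample size. Exact tests are slightly conservative, and the penalised model may need an add-on to SPSS.
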